 - a. Intermittent furosemide diuretic therapy from above (1.) with the addition of dopamine at 3 µg/kg/min
4. Continuous infusion furosemide diuretic therapy plus infusion of low dose intravenous dopamine (3 µg/kg/min)
 - a. Continuous furosemide diuretic therapy from above (2.) with the addition of dopamine at 3 µg/kg/min

Conversion guidelines:

2 mg oral furosemide = 1 mg intravenous furosemide

1 mg torsemide = 2 mg furosemide

1 mg bumetanide = 40 mg furosemide

Diuretic titration guidelines:

Should the patient fail to demonstrate adequate diuresis (net negative urine output of at least 500ml in 12 hrs) in response to the first treatment dose, the subsequent diuretic dose to be administered 12 hrs later (dose #2) will be doubled, or the continuous infusion will be doubled, with the goal of net negative urine output of 1 liter over 24 hrs. This titration plan can continue until adequate diuresis is achieved (at least net negative 1L urine output over 24 hr period).

Maximum Diuretic Dose:

The maximum dose permitted within study protocol will be furosemide 200 IV twice daily, or a total dose of furosemide 400 IV over 24 hrs. Should the primary team feel the patient needs higher dosing or the addition of a thiazide diuretic (or alternative agent), the patient will be considered treatment failure and will be removed from the study.

Electrolyte Repletion Guidelines:

The primary team will obtain basic metabolic panels on all study participants every 12 hours for the duration of the study. It will be the responsibility of the primary team to replete electrolytes with the goals of potassium > 4.0, and magnesium >2.0 as needed for study participants.

Fluid and Salt Restrictions:

Each study participant will be maintained on a daily 2 liter fluid and 2 gm sodium restricted diet, to be ordered by the primary team.

Treatment beyond trial end-point guidelines:

Intravenous diuretic therapy with or without dopamine according to the protocol will be continued until the treating physician decides the patient no longer requires intravenous diuretic therapy or 72 hours, whichever comes first.

All other heart failure or non-heart failure treatments will be left to the discretion of the primary team from the time of the patient's admission to the hospital and/or enrollment in the study. This includes anti-hypertensives, anti-arrhythmic drugs, and any other therapies deemed necessary for the treatment of the study subject.

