After 72 hrs, the study drug will be discontinued, a primary assessment will be made of primary and secondary endpoints, and all further treatment is at the treating physician's discretion.

Note: Study participants will be permitted to cross over into non-assigned arms of the study, however the study analysis will be completed as an intention-to-treat study. It will be left to the discretion of the primary team, with supervision from the study investigators as to whether a cross over is necessary within the 72 hr study time frame.

Baseline Assessments and Data to be Recorded (all are standard of care unless indicated by *)

1. Directed history and physical exam, focused on signs and symptoms of congestion/volume overload
2. Vital signs (HR, BP, O2 saturation, weight, height)
3. Home medications
4. Basic metabolic panel including serum creatinine, BUN, electrolytes and magnesium
5. Serum Pro-BNP level
6. Serum Cystatin C*
7. High-sensitivity troponin
8. Baseline electrocardiogram
9. Transthoracic echocardiogram if one has not been obtained within 1 year prior to admission
 - i. Including left ventricular (LV) ejection fraction, LV dimensions, left atrium size (LA), LV mass, right ventricular function parameters (RVSP), valvular assessment
10. 6 min walk test*
11. Patient Global Well being assessment by VAS*
12. Dyspnea assessment by VAS*
13. Frailty Index*
14. Blood sample for biomarkers and genetic testing for heart failure*
15. Urine sample for biomarkers*

24 hr Assessment:

1. Routine vitals assessment with weight recording
2. I/O assessment – to be recorded and totaled for each 12 period
3. Twice daily basic metabolic panel and serum magnesium

72 hr Assessment and Data to be Recorded:

1. Routine vitals assessment with weight recording
2. I/O assessment – to be recorded and totaled for each 24 period
3. Twice daily basic metabolic panel and serum magnesium
4. Serum Pro-BNP level*
5. Serum Cystatin C*
6. High-sensitivity troponin
7. 6 min walk test*
8. Patient Global Well being assessment by VAS*
9. Dyspnea assessment by VAS*
10. Frailty Index*
11. Changes in cardiovascular medications
12. Assessment for serious cardiovascular events

At Discharge Assessment and Data to be recorded:

1. Routine vitals assessment with discharge weight recording
2. I/O assessment – to be recorded and totaled for each 24 period
3. Basic metabolic panel including creatinine, BUN
4. Serum Pro-BNP level
5. Serum Cystatin C*
6. High-sensitivity troponin
7. 6 min walk test*

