8. Patient Global Well being assessment by VAS*
9. Dyspnea assessment by VAS*
10. Frailty Index*
11. Changes in cardiovascular medications
12. Assessment for serious cardiovascular events
13. Urine and serum samples for biomarkers*

*Investigational data to be collected as part of trial protocol.

Day 30, 6 month, and 1 year Assessment and Data to be Recorded:

Patient charts will be reviewed and patients will receive a phone call to assess for potential re-hospitalizations and major adverse cardiovascular events at each respective endpoint since discharge. The first readmission event following index hospitalization will be adjudicated by a Clinical Event Committee consisting of 2-3 cardiologists not directly in contact with patients enrolled in the study.

Vascular Access:

All patients in the intermittent bolus diuretic strategy arm will require the placement of two functioning peripheral IV catheter. Patients assigned to the continuous diuretic strategy and either treatment arm that requires low-dose dopamine will need at least 2 peripheral IVs suitable for continuous infusions. Central venous catheter placement may be required should it be difficult to obtain or maintain peripheral IV

access. This would be determined by the primary team, with consent obtained separately for this procedure by the primary team.

Foley Catheter Placement:

All patients enrolled in this trial will be encouraged to have a foley urinary catheter placed. This will allow for improved patient tolerance of diuresis and improved accuracy of I/O assessment by nursing staff. This will not be required, however, for enrollment in the trial.

b. Study duration and number of study visits required of research participants.

The study duration is the hospital admission. The study drugs will be mandated for 72 hours following enrollment. There are no outpatient visits but patients will receive follow up phone calls, at 30 days and at 6 months following discharge.

c. Blinding, including justification for blinding or not blinding the trial, if applicable.

The treatment is not blinded. The primary endpoint of change in renal function will be objectively obtained and should not be affected by lack of blinding. All other variables will be obtained by an investigator blinded to the study drug assignment.

d. Justification of why participants will not receive routine care or will have current therapy stopped.

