Participants will receive routine care for their acute decompensated heart failure. Currently, many practitioners utilize both intermittent and continuous furosemide infusions in this patient group. Low dose, or renal-dose dopamine is also a frequent adjunct to diuretics to aid in diuresis.

e. Justification for inclusion of a placebo or non-treatment group.

There is no placebo group.

f. Definition of treatment failure or participant removal criteria.

Subjects will be removed from the protocol for:

1. The development of hemodynamic instability including hypotension (SBP < 90), hypertensive emergency, or unstable arrhythmias (SVT or VT).
2. The development of pulmonary edema requiring inotropes or vasopressor or more than 50% inspired oxygen.
3. The development of acute coronary syndrome.
4. The development of acute kidney injury by KDIGO criteria as follows¹:
 - a. If the patient develops Stage II AKI (by KDIGO criteria), the study treatment will be held and a clinical decision will be made whether to resume or discontinue treatment drug
 - b. If the patient develops Stage III AKI (by KDIGO criteria), the study treatment will be discontinued and the patient will be classified as treatment failure and followed only for outcome recording.
5. The need for renal replacement therapy
6. New atrial fibrillation or other supraventricular tachyarrhythmia
7. Sustained ventricular arrhythmias

8. Requirement of furosemide dose increase beyond the study maximum of 200 IV twice daily (or 400 IV over 24 hrs), or the need for addition of thiazide diuretic.

g. Description of what happens to participants receiving therapy when study ends or if a participant's participation in the study ends prematurely.

Once the study period ends, or if the study ends prematurely, the patient will receive standard heart failure management at the discretion of the primary team. The patient will resume standard outpatient follow up as advised by the primary team at the time of discharge.

5. Inclusion/Exclusion Criteria

a. Inclusion Criteria :

1. Admission to the hospital for acute decompensated heart failure within 24 hours of enrollment into the study.
 - a. Diagnosis of heart failure as defined by the presence of at least 1 symptom (dyspnea, orthopnea, or edema) AND 1 sign (rales on auscultation, elevated jugular venous pulse, hepatojugular reflex, peripheral edema, ascites, pulmonary vascular congestion on chest radiography)
2. Patient ≥ 18 years of age

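### Intention-to-treat is promised, but the removal wording can be read as ending follow-up, and outcome recording after removal is explicit only for Stage III AKI

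*Combined protocol and SAP*

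**What the plan says.** **Analysis set.** Section 7 (Analysis of Primary Endpoints) makes the primary analysis intention-to-treat without exception. The crossover note in Section 4.a lets patients change arms, "however the study analysis will be completed as an intention-to-treat study". Neither place mentions removed patients, defines the analysis set or gives a missing-data rule.

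**Removal.** Three wordings are used.
- Section 4.a, Maximum Diuretic Dose: "Should the primary team feel the patient needs higher dosing or the addition of a thiazide diuretic (or alternative agent"), then "the patient will be considered treatment failure and will be removed from the study".
- Section 4.f: "Subjects will be removed from the protocol for" eight listed criteria, the last being the same dose-cap or added-thiazide event.
- Section 7, Early stopping rules: largely the same list, as removal from the trial.

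**AKI entries in both lists.** For Stage II, treatment is held and a decision follows on resuming or stopping. For Stage III, "the study treatment will be discontinued and the patient will be classified as treatment failure and followed only for outcome recording".

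**Text bearing on follow-up.** Early stopping rules closes by saying that the investigators report adverse events to the IRB and keep following the patients concerned while the study lasts. Section 4.b adds: "The study duration is the hospital admission". Section 4.a also states: "The primary team will obtain basic metabolic panels on all study participants every 12 hours for the duration of the study". Section 8.b describes twice-daily panels as standard of care. Section 4.g, on premature end of participation, covers clinical care only.

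**The concern.** Intention-to-treat needs an outcome for each randomised patient, or a stated way of handling its absence. If removal means leaving the study, the comparison is restricted to patients selected by events after randomisation. Some of those events may be related to the creatinine endpoint.

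The dose-cap or added-agent criterion is the most exposed. In Section 4.a it depends partly on the primary team's opinion, and Section 4.c says: "The treatment is not blinded". That section argues that an objective endpoint is safe from the lack of blinding. The argument protects how creatinine is measured, not who remains to be measured.

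At stake are power, if removals exceed the drop-out allowance, and bias in the primary comparison, if removal is related to creatinine and differs by arm.

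**Working it through.** **Step 1. The criteria side by side.**

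| Event | Consequence stated | Outcome recording stated |
|---|---|---|
| Dose above maximum, or added agent | Out of the study (4.a), the protocol (4.f), the trial (7) | Not by name |
| Haemodynamic instability, pulmonary edema needing support, acute coronary syndrome, new atrial fibrillation or SVT, sustained ventricular arrhythmia | Out of the protocol (4.f), the trial (7) | Not by name |
| Stage III AKI | Treatment discontinued, treatment failure | Yes |
| Renal replacement therapy | Listed separately in 4.f, but its initiation is Stage 3 in the protocol's KDIGO table | Yes, through Stage III |
| Stage II AKI | Treatment held, may resume; not a removal | Not stated |
| Dopamine ended for tachycardia (8.b) | Treatment failure; no removal wording | Not stated |

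The gap is therefore the first two rows. The last two rows are not removals, but how those patients are analysed is also left unsaid.

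**Step 2. The plan's own figures.** The 63 per group (no dopamine v dopamine) cannot be derived from the stated inputs, because no SD is given. It matches a standardised difference of 0.5: 2 × (1.960 + 0.842)² / 0.5² = 62.8, rounded up to 63. For the stated 30% difference that implies an SD of about 30 / 0.5 = 60 points. The drop-out allowance is 140 − 126 = 14, and 14/140 = 10%; equivalently 63 / 0.90 = 70.

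**Step 3. Power.** Normal approximation, Φ(0.5 × √(n/2) − 1.960), with n analysed per group:
- n = 70, all analysed: Φ(0.998) = 84%
- n = 63, 10% lost: Φ(0.846) = 80%
- n = 56, 20% lost: Φ(0.686) = 75%

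A 10% loss lands on the planned position. Power falls below plan only if removals are added to other drop-out, for example 70 − 7 − 7 = 56.

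**Step 4. Bias, illustration only.** Assumed: mean creatinine rise of 20 points without dopamine and 5 with it, SD 30 (again 0.5 SD), normal outcomes, 70 per group, two-sided Wilcoxon test at 0.05, 15,000 simulated trials per case. The chance of being removed and not analysed is logistic in the patient's outcome, with slope in log-odds per SD.

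| Removed, no dopamine v dopamine | Slope | Difference (points) | Power |
|---|---|---|---|
| None | – | 15.0 | 82% |
| 10% v 10% | 0 | 15.0 | 77% |
| 13% v 7% | 0 | 15.0 | 77% |
| 10.0% v 8.0%, one rule for both arms | 0.5 | 14.7 | 77% |
| 10.0% v 6.6%, one rule for both arms | 1 | 14.1 | 76% |
| 13% v 7%, arm-specific | 0.5 | 14.2 | 74% |
| 13% v 7%, arm-specific | 1 | 13.5 | 72% |
| 7% v 13%, arm-specific | 0.5 | 15.9 | 83% |
| 7% v 13%, arm-specific | 1 | 16.6 | 87% |

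The arm-specific cases need an extra shift in removal log-odds (no dopamine minus dopamine): +0.45 and +0.25 for 13% v 7%, and −0.95 and −1.25 for 7% v 13%, at slopes 0.5 and 1.

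With no true effect, unequal removal unrelated to outcome gives essentially no difference (0.0 to 0.1 points, 5.1% false positives). Unequal, outcome-related removal gives a spurious 0.8 to 0.9 points (5.4%) at slope 0.5 and 1.5 to 1.6 points (6.0% to 6.1%) at slope 1, in either direction. With no true effect, one common rule gives no bias.

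**The case against.** The best defence is that the lists govern study treatment, not data. Section 4.a heads the four regimens as the treatment protocol, so removal from the protocol reads naturally as stopping treatment. Both AKI entries are about treatment, and Stage III patients are expressly followed although they sit inside a removal list. The follow-up sentence comes directly after the dose-cap item in Section 7. Intention-to-treat is stated without exception, and crossover shows that departures from assigned treatment were foreseen. Because inpatient panels are routine, a 72-hour creatinine will usually exist.

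Much of this stands. Removal cannot always mean that data collection ends, and the follow-up sentence may cover the other criteria. But that sentence concerns adverse-event reporting and names no endpoint, and a value in the chart is not a commitment to analyse it. Naming outcome recording for Stage III alone leaves the other criteria open.

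The judgement element is also only partial: Sections 4.f and 7 speak of a requirement for a higher dose, and Section 4.a gives a numerical titration trigger of 500 ml net in 12 hours.

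A reader might infer more than the documents support:
- **That removed patients will be left out of the primary analysis.** No passage says so.
- **That every listed criterion ends follow-up.** Stage II is a hold, and Stage III, with renal replacement, is followed.
- **That the largest creatinine rises would be deleted**, inflating false positives far more than shown above. Those same AKI rules run against it.
- **That removal will favour one arm.** The Background reports more urine output with dopamine but no significant effect on adverse outcomes, while Section 8.a lists fast or irregular heart rates as a dopamine risk. Neither shows that removal will differ by arm, or in which direction.

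**Conclusion.** The contradiction holds and should be fixed. Two of the three removal wordings, read literally, conflict with the stated intention-to-treat analysis. For patients removed under criteria other than Stage III AKI, no passage commits to recording and analysing the 72-hour creatinine.

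This is a wording conflict, not a demonstrated bias. If every patient's routine creatinine is analysed as randomised, the problem does not arise. If the removal wording is followed instead, the size is unknown. The illustration suggests a modest effect at about 10% removal, growing with more, or more unequal, removal. It rests on an assumed SD, effect, removal rate and link between removal and creatinine, none of which the documents give. Confidence is medium, because the intended meaning of removal cannot be settled from the text.

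**What to change.** Reconcile Section 4.a (Maximum Diuretic Dose), Section 4.f and Section 7 (Early stopping rules). For criteria that end study treatment, say that removal means stopping study treatment and not leaving follow-up. Apply the outcome-recording commitment now given for Stage III AKI to those criteria, including the dose-cap or added-agent one.

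In Section 7, state that the 72-hour creatinine from the routine panels is recorded for every randomised patient and analysed as randomised. Include patients whose treatment is held for Stage II AKI or whose dopamine is stopped for tachycardia. All clinical criteria, including the Stage II hold-and-resume rule, stay as they are.

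The cost is a protocol wording change, since the panels are already standard of care. If the starred research assessments, such as cystatin C and the walk test, are also continued after removal, they need some staff time. Values taken after treatment stops may dilute the contrast between arms, which intention-to-treat already accepts.

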Secondary end points:

1. Change in incidence of acute kidney injury (AKI) as defined by Kidney Disease: Improving Global Outcomes (KDIGO criteria summarized below) from randomization to 72 hrs.¹

2. Incidence of AKI as determined by urine output at 72 hrs (KDIGO criteria, summarized below).¹
3. Change in creatinine at 72 hrs adjusted for volume of fluid removal
4. Change in serum cystatin C randomization to 72 hrs
5. Change in NT pro-BNP from randomization to 72 hrs
6. Volume of diuresis measured in liters
 - a) Cumulative volume of diuresis measured in liters
 - b) Cumulative volume of diuresis measured in liters adjusted for BSA
7. Net weight loss at 72 hrs in kg
8. Need for increase in intravenous diuretic dose
9. Change in distance during 6 minute walk test
 - a) From admission to 72 hrs
 - b) From admission to discharge
10. Global well-being assessment score from admission to 72 hrs, and at discharge. To be assessed by a Visual Analog Scale (VAS).
11. Subjective dyspnea score from admission to 72 hrs, and at discharge. To be assessed by a Visual Analog Scale (VAS).
12. Change in frailty index from admission to 72 hrs, and at discharge. To be assessed by the Johns Hopkins Older Americans Independence Center Online Frailty Assessment Tool
13. Length of stay of hospitalization in days
14. 30 day, 6 month, and 1 year hospital readmission or ER visit for major adverse cardiovascular event, heart failure, renal failure (development of CKD, ESRD, or dialysis need by KDIGO criteria), syncope, or arrhythmia. Readmission events will be adjudicated by a Clinical Event Committee consisting of 2-3 cardiologists not directly in contact with patients enrolled in the study.

KDIGO AKI Definition¹:

AKI is defined by any of the following 3 criteria:

1. Increase in serum creatinine by ≥ 0.3 mg/dl (≥ 26.5 $\mu\text{mol/l}$) within 48 hours; OR
2. Increase in serum creatinine to ≥ 1.5 times baseline, which is known or presumed to have occurred within prior 7 days; OR
3. Urine volume < 0.5 ml/kg/h for 6 hours

Stages of AKI as defined by KDIGO Criteria are as follows:

Stage	Serum Creatinine	Urine Output
1	1.5-1.9 times baseline OR ≥ 0.3 mg/dl (≥ 26.5 $\mu\text{mol/l}$) increase	< 0.5 ml/kg/h for 6-12 hours

2	2.0-2.9 times baseline	<0.5 ml/kg/h for \geq 12 hours

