14. 30 day, 6 month, and 1 year hospital readmission or ER visit for major adverse cardiovascular event, heart failure, renal failure (development of CKD, ESRD, or dialysis need by KDIGO criteria), syncope, or arrhythmia. Readmission events will be adjudicated by a Clinical Event Committee consisting of 2-3 cardiologists not directly in contact with patients enrolled in the study.

KDIGO AKI Definition¹:

AKI is defined by any of the following 3 criteria:

1. Increase in serum creatinine by ≥ 0.3 mg/dl (≥ 26.5 $\mu\text{mol/l}$) within 48 hours; OR
2. Increase in serum creatinine to ≥ 1.5 times baseline, which is known or presumed to have occurred within prior 7 days; OR
3. Urine volume < 0.5 ml/kg/h for 6 hours

Stages of AKI as defined by KDIGO Criteria are as follows:

Stage	Serum Creatinine	Urine Output
1	1.5-1.9 times baseline OR ≥ 0.3 mg/dl (≥ 26.5 $\mu\text{mol/l}$) increase	< 0.5 ml/kg/h for 6-12 hours
2	2.0-2.9 times baseline	< 0.5 ml/kg/h for ≥ 12 hours
3	3.0 times baseline OR increase in serum creatinine to ≥ 4.0 mg/dl (≥ 353.6 $\mu\text{mol/l}$) OR initiation of renal replacement therapy OR, in patients < 18 years, decrease in eGFR to < 35 ml/min per 1.73 m ²	< 0.3 ml/kg/h for ≥ 24 hours OR Anuria for ≥ 12 hours

a. Statistical plan including sample size justification and interim data analysis.

1. Overview:

- a. This is a factorial design study evaluating two simultaneous unrelated interventions. Sample size justification and primary endpoint analysis is described below.

2. Analysis of Primary Endpoints:

- a. The primary analysis will be conducted on an intention-to-treat basis. Non-parametric testing for the continuous primary endpoint (creatinine) will be performed using the Wilcoxon-Mann-Whitney U test. Confirmatory test for interaction between dopamine and diuretic strategy will be performed with linear regression analysis with dopamine*diuretic term, $p=0.10$ for significance.

3. Sample Size Justification:

- a. A difference of 30% in creatinine pre and post- treatment is considered to be clinically meaningful. Setting parameters as follows: two-sided, alpha (Type I error rate) of 0.05, power of 0.80, and using mean creatinine calculations based on our own retrospective experience at

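### Urine-output AKI is defined over 6 hours, but urine is scheduled to be totalled only per 12 h and then per 24 h, so deriving secondary endpoint 2 from those totals under-counts cases

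*Combined protocol and SAP*

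**What the plan says.** **Definition.** Sections 2 and 7.b state that "AKI is defined by any of the following 3 criteria", the third being "Urine volume < 0.5 ml/kg/h for 6 hours". In the staging table the urine criterion for Stage 2 is "< 0.5 ml/kg/h for ≥ 12 hours".

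**Endpoints.** Secondary endpoint 2 is "Incidence of AKI as determined by urine output at 72 hrs". Secondary endpoint 1 is "Change in incidence of acute kidney injury (AKI) as defined by Kidney Disease: Improving Global Outcomes", from randomization to 72 h, with no restriction to the creatinine criteria.

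**Data schedule (Section 4.a).** At the 24 h assessment: "I/O assessment – to be recorded and totaled for each 12 period". At the 72 h assessment, and again at discharge: "I/O assessment – to be recorded and totaled for each 24 period". The unit is missing, but hours are clearly meant. I/O carries no asterisk, so it is routine care and not an investigational measurement. Section 4.a encourages a urinary catheter but does not require one.

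**Use during treatment (Section 4.f).** "If the patient develops Stage II AKI (by KDIGO criteria), the study treatment will be held and a clinical decision will be made" on whether to resume or stop.

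The plan does not ask for 6 h or hourly urine volumes, and it does not say how endpoint 2 is to be derived from the I/O record.

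**The concern.** The window in the definition is shorter than any window that the protocol schedules to be totalled. A total is an average over its block, so a low stretch can be offset by a higher one in the same block. If the analysis uses the scheduled totals, endpoint 2 no longer measures the stated criterion. It measures a stricter one: a mean below the limit over 12 h on day 1, and over 24 h after that.

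The endpoint also sits close to a randomised comparison. One factor is 12-hourly bolus against continuous infusion. Each day-1 total spans a full dosing interval and each later total spans two, so any difference between arms in the timing of urine within the interval is averaged out. Whether such a difference exists is not stated in the documents.

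**Working it through.** The plan states no figure to reproduce. The check compares windows, then does arithmetic on the threshold.

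**Inputs from the documents.** Limit 0.5 ml/kg/h over 6 h, and over 12 h for Stage 2 (7.b). Totals per 12 h on day 1 and per 24 h to 72 h (4.a). Diuresis goal of net −1 L per 24 h and a 2 L daily fluid restriction (4.a). **Assumption:** body weight 80 kg. The criterion is read as mean output over the window.

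**1. Windows.** 72/6 = 12 six-hour blocks and 72/12 = 6 twelve-hour blocks. The schedule gives 2 × 12 h + 2 × 24 h = 4 totals. None of the 12 six-hour blocks is totalled, and only 2 of the 6 twelve-hour blocks are.

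**2. Limits.** 0.5 × 6 = 3 ml/kg; 0.5 × 12 = 6 ml/kg; 0.5 × 24 = 12 ml/kg. At 80 kg these are 240, 480 and 960 ml.

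**3. What a total can hide.** If 6 h run at rate r, the block mean still reaches 0.5 when the rest averages at least
- 12 h block: (6 − 6r)/6
- 24 h block: (12 − 6r)/18

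| r (ml/kg/h) | other 6 h of a 12 h block | other 18 h of a 24 h block |
|---|---|---|
| 0.4 | 0.60 | 0.53 |
| 0.2 | 0.80 | 0.60 |
| 0 | 1.00 | 0.67 |

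**4. Direction.** With complete collection, a 12 h total below 6 ml/kg or a 24 h total below 12 ml/kg implies at least one 6 h block below 3 ml/kg. Totals then miss cases but create none. If voids are lost, recorded volumes are too low and false cases become possible.

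**5. A patient at the diuresis goal.** With 2 L intake and net −1 L, urine is 3000 ml, or 3000/(24 × 80) = 1.56 ml/kg/h. Six hours at 0.4 ml/kg/h is 192 ml, below 240 ml, so the criterion is met. The other 18 h carry 2808 ml (1.95 ml/kg/h) and the 24 h total looks normal. In general, at the goal a 24 h total cannot flag anyone up to (1000 + intake)/12 kg: 83.3 kg with no intake, 125 kg with 500 ml, 166.7 kg with 1 L and 250 kg with 2 L.

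**6. Stage 2.** At 80 kg, 1550 ml then 450 ml gives 450/(12 × 80) = 0.47 ml/kg/h in the second 12 h, which meets Stage 2. The 24 h mean is 2000/(24 × 80) = 1.04.

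**7. Illustration of size; every input is an assumption.** 200,000 simulated patients of 85 kg; log-normal daily output with between-patient CV 35%; 6 h CV 20%; a share f of each 12 h output falling in the first 6 h.

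| Median output per 24 h | f | criterion met | flagged by scheduled totals |
|---|---|---|---|
| 2.0 L | 0.5 | 17.8% | 6.2% |
| 2.0 L | 0.7 | 61.6% | 6.6% |
| 2.5 L | 0.5 | 6.1% | 1.5% |
| 2.5 L | 0.7 | 37.5% | 1.7% |
| 3.0 L | 0.5 | 2.1% | 0.4% |
| 3.0 L | 0.7 | 20.6% | 0.4% |

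Centring the noise differently moves these slightly (5.5% and 35.7% met at 2.5 L). Out of 140 patients, the missed cases run from (2.1 − 0.4)% × 140 ≈ 2 to (61.6 − 6.6)% × 140 = 77. A range that wide shows that the documents cannot settle the size.

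**The case against.** **The data may exist.** Section 4.a has I/O both recorded and totalled, and the stated period can be read as applying only to the totalling. I/O is routine nursing charting, so finer entries may be available. This stands. A reader might infer that endpoint 2 cannot be derived at all, and the text does not show that. It shows that the protocol neither requires finer entries nor makes them study data, and that their resolution may vary with catheter use.

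**Blinding.** A reader might infer that going back to ward charts in an open-label trial would bias the endpoint. Sections 4.a and 4.c say that outcome collection is blinded and that variables other than the primary endpoint are obtained by a blinded investigator. That answers much of this worry, though not the dependence on catheter use.

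**Endpoint 1.** Listing urine-output AKI separately suggests that endpoint 1 was meant as the creatinine version. That is plausible. Read literally, endpoint 1 includes the urine criterion, but only as one of three, and the other two are served by 12-hourly metabolic panels.

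**Bias between diuretic arms.** It is tempting to conclude that totals would mask a bolus-against-continuous difference. That needs output to be front-loaded after a bolus, and the documents give no output profile. With even output at 3 L per 24 h, the illustrated gap is about 2 patients in 140.

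**Safety.** A reader might infer that the Stage II hold cannot be applied. The hold is a bedside decision, and titration already involves a 12 h output check. The scheduled totals after day 1 cannot document whether the urine criterion was met, but that does not show that staff would miss it.

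**Conclusion.** The mismatch is in the text and holds. Secondary endpoint 2 rests on a 6 h window and the scheduled totals cover 12 h and 24 h, so deriving it from those totals under-counts cases. The direction follows from arithmetic, provided that urine collection is complete and the criterion is read as a 6 h mean. The magnitude is unknown: in the illustration the totals miss roughly 65% (1 − 6.2/17.8) to 98% (1 − 0.4/20.6) of true cases, but in absolute terms this can be small or large. No claim of bias between arms is supported.

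The reach is limited to endpoint 2, plus the urine component of endpoint 1 on a literal reading. The primary creatinine endpoint is untouched. It is worth correcting because the repair is cheap, and 6 h volumes charted nowhere during the 72 h cannot be recovered later.

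**What to change.** **Section 4.a.** Record urine output for each 6 h period from start of study treatment to 72 h in all four arms, extracted from nursing charts by the blinded assessor. Sum these periods for the 12 h titration check and the volume endpoints.

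**Section 7.b.** State that endpoint 2 is met if any 6 h period is below 3 ml/kg of baseline weight. State that urine-output Stage 2 is met if any two consecutive 6 h periods sum to less than 6 ml/kg. Do not require each of the two to be below 3 ml/kg: at 80 kg, 250 + 200 ml is 450 ml (0.47 ml/kg/h over 12 h, below the 480 ml limit), yet the first period exceeds 240 ml and such a rule would miss it. In the illustration at 2.5 L and f = 0.7, that rule flags 0.4% of patients, against 2.4% by 12 h sums. Say also whether endpoint 1 includes the urine criterion.

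**Incomplete collection.** Mark such periods as missing, not low, and report endpoint 2 by catheter use.

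**Cost.** Up to 12 entries per patient in place of 4 totals, at most 12 × 140 = 1,680 in all, with no added samples or visits. Two limits remain: fixed blocks can still miss a low run that straddles two of them, and uncollected voids can produce false low periods in patients without a catheter.
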